Concomitant Medications		Conti	nuous from si	gning ICF until 30 days after last dose of study therapy		
Subsequent Anticancer Therapy					X	x
AESI, irAEs and SAEs	Continuous from signing ICF until 90 days after last dose of study therapy or resolution/stabilization					
Hematology 3,4	Х	C1D1	C2D1	C3D1 then Q6W (ie, at every other visit) and as clinically indicated	Х	
Chemistry ^{3,4}	Х	C1D1	C2D1	C3D1 then Q6W (ie, at every other visit) and as clinically indicated	Х	
INR, PT, PTT (or aPTT)	Х	As clinically indicated				
Thyroid Monitoring 3,5	Х	Q6W (±7D) and as clinically indicated				
Pregnancy Test ^{3,6}	≤2D before C1D1	Q12W (±14D)				

Confidential Page 20 of 109

Cutaneous, Subcutaneous and Nodal Lesion Measurement and Photographs ^{3,7}	Х	C1D1, C1D8, C1D15	C2D1, C2D8, C2D15	Day 1 of each Cycle	х	per SOC
Tumor Imaging ⁸	≤6W before C1D1	6 & 12W after C1D1, then Q12W thereafter. Crossover participants must have re-baseline imaging within 28D prior to administration of crossover C1D1 (i.e. first dose of anti-PD-1 therapy)				
Tissue Biopsy ⁹ All samples to be collected prior to dosing at the given timepoint	Prior to PV Immunization Booster	C1D8	C2D1	At the time of PD ± 1 week (per RECIST) Crossover Only: within 1 week prior to crossover C1D1, 1 week after crossover C1D1 (pre-dose, if applicable), 3 weeks (+7d; pre-dose) after crossover C1D1, and at the time of PD ± 1 week (per RECIST) on the crossover regimen		
Blood Collection ¹⁰ All samples to be collected prior to dosing at the given timepoint	Prior to PV Immunization Booster	C1D1, C1D8	C2D1	C3D1 and at the time of PD ± 1 week (per RECIST) Crossover Only: within 1 week prior to crossover C1D1, 1 week after crossover C1D1 (pre-dose, if applicable), 3 weeks (+7d; pre-dose) after crossover C1D1, and at the time of PD ± 1 week (per RECIST) on the crossover regimen		
Lerapolturev Administration ¹²		C1D1, C1D8, C1D15	C2D1, C2D8, C2D15	C3D1 and Q3W thereafter		
ARM 2: Anti-PD-1 Administration (pembrolizumab)		C1D1	C2D1 (if given Q3W)	C3D1 and Q3W or Q6W thereafter per pembrolizumab package insert		
Crossover from Arm 1 to Arm 2 13		If participant meets protocol-defined criteria				
Lerapolturev Shedding: Injected Lesion ¹⁴		C1D1 (post- injection), C1D4, C1D8, C1D15 (post- injection), C1D18	C2D1, C2D15 (post- injection), C2D18	C3D1		
Lerapolturev Shedding: Stool			C2D8 (±3D)			

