AESI = adverse event of special interest; aPTT = activated partial thromboplastin time; C= cycle; CBC = complete blood count; CMP = comprehensive metabolic panel; CT = computed tomography; D = day; ECOG = Eastern Cooperative Oncology Group; EOT = End of Treatment; ICF = Informed consent form; IgG = immunoglobulin G; INR = international normalized ratio; LDH = lactate dehydrogenase; MRI = magnetic resonance imaging; PD-1 = Programmed cell death protein 1; PT = prothrombin time; PTT = partial thromboplastin time; PV = poliovirus; T3 = triiodothyronine; T4 = thyroxine; TSH = thyroid stimulating hormone; SAE = serious adverse event; W = weeks

1. Informed Consent must be signed prior to initiation of screening activities.

Confidential Page 21 of 109

- 2. Physical Exam: The screening physical examination should be a complete physical exam of major body systems and include the general appearance of the participant, height and weight, vital signs (temperature, respiratory rate, blood pressure (systolic and diastolic [mmHg]), and heart rate [bpm]), examination of the skin, ears, nose, throat, lungs, heart, abdomen, extremities, musculoskeletal system, lymphatic system, and nervous system. During treatment and at the end of treatment (EOT) visit, weight assessment and limited symptom-directed physical examination are required. An evaluation of all skin lesions, including those injected with lerapolturev at the previous treatment visit, should be performed prior to subsequent lerapolturev injection.
- 3. Procedures and/or Assessments unless otherwise specified should occur on D1 of each Cycle. Any assessment or procedure scheduled on the same day as lerapolturev and/or anti-PD-1 administration should always precede receipt of study treatments. Note that laboratory assessments (e.g. hematology, chemistry, thyroid monitoring) may be done up to 2 calendar days prior to Day 1 of the cycle.
- 4. Hematology and Chemistry: Blood draws for hematology and chemistry occurring on the same day as study treatment should be collected prior to lerapolturev injection and/or prior to anti-PD-1 infusion (as applicable). Hematology should include hemoglobin, white blood cell (WBC) count with differential and platelet count. Chemistry measured in serum should include the following: LDH, glucose, calcium, sodium, potassium, bicarbonate, chloride, BUN, creatinine, total protein, albumin, ALP, AST, ALT, total bilirubin, amylase, and lipase.

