- **15. End of Treatment Visit** should be performed within 28 days after the last dose of study drug(s). The visit should include a focused and symptom-directed physical assessment, cutaneous, subcutaneous, and nodal tumor measurements (including photographs), as well as radiographic tumor imaging.
- 16. Survival Follow-up: Scans and cutaneous, subcutaneous and nodal lesion measurements performed per SOC should still be collected for participants in post-EOT survival follow-up who discontinued study treatments for reasons other than disease progression. The collection of lesion measurement (cutaneous, subcutaneous, and nodal, and scans) performed per SOC should continue until confirmed progression or the start of the next anti-cancer therapy. Sites should continue to collect post-study therapies and survival status for follow-up duration

Confidential Page 24 of 109

Table 2. Schedule of Assessments for Lerapolturev + Nivolumab

NOTE: Cycle length for lerapolturev + nivolumab is 4 weeks. Lerapolturev is administered weekly during Cycles 1 & 2 and every 4 weeks thereafter on the days indicated in the table below. Refer to the table below for the timing of other study assessments to be completed within each cycle.

	Screening Period	Treatment				Survival Follow- up ¹⁶	
Study Procedure ³		Cycle 1	Cycle 2	≥ Cycle 3			
	(≤ 28D prior to C1D1)		+4W (+7D)	Q4W (+7D)	≤28D after last treatment		
Informed Consent ¹	X						
Medical History	X						
Physical Exam ^{2,3}	X	C1D1	C2D1	Day 1 of each Cycle	X		
Vital Signs ³	x	C1D1, C1D8, C1D15 C1D22	C2D1, C2D8, C2D15	Day 1 of each Cycle	X		
ECOG Performance Status ³	X	C1D1	C2D1	Day 1 of each Cycle	Х		
PV Immunization Booster ¹	≥1W, but ≤6W before C1D1						
Adverse Events		Continuous from signing ICF until 30 days after last dose of study therapy					
Concomitant Medications		Continuous from signing ICF until 30 days after last dose of study therapy					
Subsequent Anticancer Therapy					Х	×	
AESI, irAEs and SAEs	Contin	Continuous from signing ICF until 90 days after last dose of study therapy or resolution/stabilization					
Hematology 3,4	X	C1D1	C2D1	C3D1 then Q8W (ie, at every other visit) and as clinically indicated	Х		
Chemistry ^{3,4}	Х	C1D1	C2D1	C3D1 then Q8W (ie, at every other visit) and as clinically indicated	Х		
INR, PT, PTT (or aPTT)	Х	As clinically indicated					
Thyroid Monitoring 3,5	X		Х	Day 1 of each Cycle	X		
Pregnancy Test ⁶	≤2D before C1D1			Q12W (±14D)			

Confidential Page 25 of 109

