Any participant from the safety run-in cohort is allowed to crossover to combination therapy after completion of the safety run-in, as described in Section 3.1.1. However, these participants will be analyzed separately, and will not contribute to the population enrolled to establish the anti-tumor activity of the lerapolturev/anti-PD-1 regimen.

Lerapolturev Dose, **QW** Schedule: Given the slight increase in the lerapolturev dose and increased frequency of dosing during the first 2 months on treatment, the DSMC will review all safety data once 12 participants have started the weekly x 7 "induction" series of injections (ie, n=6 monotherapy and n=6 combination with anti-PD-1) and have cleared the DLT evaluation period (ie, 21 days after Cycle 1, Day 1). Applying the same rules as used for the original safety run-in, should an excessive DLT rate (ie, >33%) be detected, the lerapolturev dose (ie, the maximum number of lesions and/or maximum TCID₅₀ dose) and/or the number of weekly injections may be decreased in one or both treatment arms, based on DSMC recommendations. See Section 3.1.4 for the DLT definitions.

Confidential Page 53 of 109

NOTE: For Arm 2 (lerapolturev/anti-PD-1 combination), AEs should only be considered a DLT if judged by the investigator to be related to lerapolturev and of increased severity/frequency compared to what is expected with administration of single-agent anti-PD-1 therapy in this population, or if it is refractory to common management practices due to lerapolturev.

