3.1.4 Definition of Dose-Limiting Toxicity

The DLT evaluation period begins on the day of first lerapolturev injection (ie, Cycle 1, Day 1) and ends 21 days later. The definition of a DLT includes any of the following treatment-emergent events that are deemed at least possibly related to lerapolturev administration:

- Any Grade 4 non-hematologic toxicity (not laboratory)
- Any Grade 3 non-hematologic toxicity (not laboratory), EXCEPT:
 - ⊙ Grade 3 fatigue lasting ≤3 days or Grade 3 fatigue in a participant with Grade 1 fatigue at baseline
 - Grade 3 diarrhea, nausea, or vomiting without use of anti-emetics or antidiarrheals per standard of care
 - Grade 3 adrenal insufficiency, hypothyroidism, or Type 1 diabetes mellitus due to suboptimal hormone replacement therapy
 - Grade 3 rash without use of corticosteroids or anti-inflammatory agents per standard of care
- Grade 3 or Grade 4 non-hematologic laboratory values ONLY if:
 - Clinically significant medical intervention is required to treat the participant, or
 - The abnormality leads to hospitalization, or
 - The abnormality persists for >1 week after intervention
 - o The abnormality results in a diagnosis of drug-induced liver injury (DILI)
 - Exceptions: Clinically nonsignificant, treatable, or reversible laboratory abnormalities including liver function tests, uric acid, etc.
- Any Grade 4 hematologic toxicity lasting ≥7 days, EXCEPT:
 - o Grade 4 thrombocytopenia of any duration
 - Grade 3 thrombocytopenia associated with bleeding that requires a platelet transfusion
- Febrile neutropenia Grade 3 or Grade 4 ONLY if:
 - Grade 3 is defined as ANC <1000/mm³ with a single temperature of >38.3
 °C (101 °F) or a sustained temperature of ≥38 °C (100.4 °F) for more than 1 hour
 - Grade 4 is defined as ANC <1000/mm³ with a single temperature of >38.3
 °C (101 °F) or a sustained temperature of ≥38 °C (100.4 °F) for more than 1 hour, with life-threatening consequences and urgent intervention indicated
- Prolonged delay (>2 weeks) in initiating the second cycle of anti-PD-1 therapy while on study due to lerapolturev-related toxicity.
- Prolonged delay (> 15 weeks) in initiating the second cycle of anti-PD-1 therapy while on study due to anti-PD-1-related toxicity (12 weeks for recovery to ≤ Grade

Confidential Page 54 of 109

1 and up to an additional 3 weeks for steroid taper of oral prednisone or equivalent to \leq 10 mg/day)

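### Protocol Section 3.1.4 as typed removes Grade 4 thrombocytopenia from the DLT count, and the 21-day QW window schedules at most one post-dose blood panel (none with nivolumab)

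*Protocol*

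**What the plan says.** Protocol Section 3.1.3 (QW schedule) has the DSMC review all safety data when 12 participants, 6 per arm, have started the weekly series "and have cleared the DLT evaluation period (ie, 21 days after Cycle 1, Day 1"). If the DLT rate exceeds 33%, the dose or the number of weekly injections may be reduced on DSMC recommendation.

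Section 3.1.4 defines the DLTs. The hematologic item reads "Any Grade 4 hematologic toxicity lasting ≥7 days, EXCEPT", and the first entry beneath it is "Grade 4 thrombocytopenia of any duration". The second entry is Grade 3 thrombocytopenia with bleeding that requires a platelet transfusion.

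In Table 1 (monotherapy or pembrolizumab) the hematology and chemistry rows list screening, C1D1 and C2D1, then "C3D1 then Q6W (ie, at every other visit) and as clinically indicated". Table 2 (nivolumab) lists the same visits, then "C3D1 then Q8W (ie, at every other visit) and as clinically indicated". Footnote 4 of both tables says: "Blood draws for hematology and chemistry occurring on the same day as study treatment should be collected prior to lerapolturev injection". Footnote 3 allows laboratory draws up to 2 days before Day 1 of a cycle. SAP Section 1.2 reproduces both schedules, and the SAP does not restate the DLT definition, so the protocol wording governs.

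**The concern.** The review clears a regimen whose per-visit maximum is 1.6 x 10^9 TCID50, against 6 x 10^8 before (a ratio of 2.67), and which is now given weekly. By Day 15 a participant can have received 3 x 1.6 x 10^9 = 4.8 x 10^9. The DLT count is a main summary in that decision.

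If the definition is followed literally, a related Grade 4 platelet count is left out of the numerator, although it is among the more serious cytopenias and matters for a drug injected into tumors. Separately, an absence of Grade 4 hematologic DLTs could partly reflect that blood was hardly drawn. The dose-hold rule in Section 5.5.1 (related Grade 3 or greater hematologic or non-hematologic toxicity) also has no scheduled laboratory value to act on before several of the injections.

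**Working it through.** The plan gives no operating figure for the DLT rule, so there is none to reproduce. The check is of wording and calendar, with C1D1 = Day 1.

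**1. The EXCEPT list.** Section 3.1.4 uses the same word under the Grade 3 non-hematologic criterion. There the items below it (short-lived fatigue, for example) are taken out of the DLT definition. Applied the same way to the hematologic criterion:
- Grade 4 thrombocytopenia of any duration is taken out, including cases lasting 7 days or more.
- Grade 3 thrombocytopenia with transfusion-requiring bleeding has nothing to be taken out of, because the criterion covers Grade 4 only.

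The second entry makes sense only as an added DLT, which suggests that both were meant that way. As typed, either event counts only through another criterion, such as discontinuation within the window or Grade 5. A severe bleed might count in its own right, but that is the bleed and not the platelet count.

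**2. Scheduled panels in the window.**
- Window end: 1 + 21 = Day 22.
- The C1D1 panel is pre-dose, so it is not a post-dose value.
- Table 1, 3-week cycle: C2D1 = 1 + 21 = Day 22; allowed from 22 - 2 = Day 20 to 22 + 7 = Day 29. This is one panel at the very end of the window, or none if the visit is late.
- Table 2, 4-week cycle: C2D1 = 1 + 28 = Day 29; allowed from 29 - 2 = Day 27 to 29 + 7 = Day 36. No panel falls in the window.

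**3. The duration criterion.** A draw on Day 20, the earliest allowed, leaves 22 - 20 = 2 days before the window closes, short of the 7 required. Section 7.2.2 has clinically significant abnormal values repeated about weekly. With that repeat, a 7-day duration is first shown on 20 + 7 = Day 27 (Table 1) or 27 + 7 = Day 34 (Table 2). Section 3.1.4 does not say whether a duration completed after Day 22 counts.

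**4. The hold rule.** Weekly injections with a scheduled panel beforehand:
- Table 1: C1D1, C2D1 and C3D1, 3 of 7. None before Days 8 and 15.
- Table 2: C1D1 and C2D1, 2 of 7. None before Days 8, 15 and 22.

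**5. What added panels would do.** Assumptions, not from the documents: onset equally likely on each of the 20 days from Day 2 to Day 21, visits on time, no unscheduled draws. A cytopenia with onset on day o and duration L covers days o to o + L - 1.

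| Duration | Seen by one panel by Day 22, Table 1 now | Table 2 now | With Days 8, 15, 22 | Seen on two of those panels |
|---|---|---|---|---|
| 7 days | 6/20 | 0/20 | 20/20 | 0/20 |
| 10 days | 9/20 | 0/20 | 20/20 | 6/20 |
| 14 days | 13/20 | 0/20 | 20/20 | 14/20 |

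Two-panel confirmation in the window is 0/20 now in both tables. The added panels would detect every such episode, but a short one would still need a repeat draw to establish its duration. The table describes the schedule. It does not estimate how many DLTs are missed.

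**The case against.** **The wording will be understood.** An investigator may read the platelet entry as an exception to the 7-day requirement, not to DLT status. That is probably the intent. But it gives EXCEPT the opposite sense from its use earlier in the same section, and anyone classifying by the text would exclude the event. The error stands, and it looks like a drafting slip, not a decision to exclude.

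**Existing safeguards cover most events.** Both tables allow draws when clinically indicated, Section 7.2.2 requires repeats, the DSMC sees all safety data, and Section 9.1.5 provides ongoing DLT review. The 17 participants treated by 10 December 2021 had no DLTs and no treatment-related Grade 3 or higher events, at the lower dose and frequency (Section 1.2.2.2). This stands for clinically evident events. It does not supply a value for a silent cytopenia that nobody measured.

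**Stronger readings that the documents do not support.**
- A reader might infer that chemistry DLTs are also being missed. Section 3.1.4 counts non-hematologic laboratory values only under conditions such as required intervention, hospitalization, a diagnosis of drug-induced liver injury, or "The abnormality persists for >1 week after intervention". A silent value that resolved unseen met none of these, so it is not a DLT missing from the count.
- A reader might infer a measurable loss of power for the 33% rule. That needs the share of DLTs that are laboratory-only, which the documents do not give. Table 4 has 5 laboratory terms among 21 lerapolturev-related preferred terms, but these are terms, not DLTs; each was reported in one run-in participant, all related events were Grade 1 or 2, and only anaemia is hematologic. Nor is the rule mechanical: the DSMC has discretion.
- A reader might infer that the delay criteria drop out, for example "Prolonged delay (>2 weeks) in initiating the second cycle of anti-PD-1 therapy while on study due to lerapolturev-related toxicity", which with pembrolizumab every 3 weeks is first met on 22 + 15 = Day 37. A held cycle is visible in the safety data at the review, earlier enrollees may already be past that day when the twelfth clears, and DLT review continues afterwards.

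**Conclusion.** The hematologic DLT criterion is wrong as written: applied literally, it leaves Grade 4 thrombocytopenia out of the count and lists a Grade 3 event as an exception to a Grade 4 rule. This rests on the text alone.

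The laboratory schedule is a lesser point and a cheap improvement. The calendar is certain: one scheduled post-dose panel at the end of the window for monotherapy and pembrolizumab, none for nivolumab, and no scheduled route to the 7-day criterion inside the window. The consequence is confined mainly to silent Grade 4 cytopenia, plus a hold rule without scheduled values early in treatment. The number of DLTs affected cannot be derived from the documents and may be close to zero if such events are rare. The point concerns the DLT count, not everything the DSMC sees.

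**What to change.** 1. **Section 3.1.4:** in the hematologic criterion, replace EXCEPT with *and also*, so that both thrombocytopenia items are DLTs. This needs no new data and can be applied when DLTs are classified and reported. If the exclusion of Grade 4 thrombocytopenia was intended, give the reason and move the Grade 3 item.

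2. **Tables 1 and 2:** add pre-injection hematology and chemistry at C1D8 and C1D15, and at C1D22 in Table 2, at least for the first 6 QW participants per arm.

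**Cost.** There are 2 extra panels per participant in Table 1 and 3 in Table 2. For the first 12 participants this is 12 x 2 = 24 if all follow Table 1, or 6 x 2 + 6 x 3 = 30 if all of Arm 2 receives nivolumab. No visits are added, since participants already attend for injection. Research blood is already drawn at C1D8 in both tables and at C1D22 in Table 2, so only C1D15 needs a new draw. Results must be back before the injection, and some incidental abnormalities will be found, although the conditions in Section 3.1.4 limit which non-hematologic values become DLTs.

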3.1.4 Definition of Dose-Limiting Toxicity

The DLT evaluation period begins on the day of first lerapolturev injection (ie, Cycle 1, Day 1) and ends 21 days later. The definition of a DLT includes any of the following treatment-emergent events that are deemed at least possibly related to lerapolturev administration:

- Any Grade 4 non-hematologic toxicity (not laboratory)
- Any Grade 3 non-hematologic toxicity (not laboratory), EXCEPT:
 - ⊙ Grade 3 fatigue lasting ≤3 days or Grade 3 fatigue in a participant with Grade 1 fatigue at baseline
 - Grade 3 diarrhea, nausea, or vomiting without use of anti-emetics or antidiarrheals per standard of care
 - Grade 3 adrenal insufficiency, hypothyroidism, or Type 1 diabetes mellitus due to suboptimal hormone replacement therapy
 - Grade 3 rash without use of corticosteroids or anti-inflammatory agents per standard of care
- Grade 3 or Grade 4 non-hematologic laboratory values ONLY if:
 - Clinically significant medical intervention is required to treat the participant, or
 - The abnormality leads to hospitalization, or
 - The abnormality persists for >1 week after intervention
 - o The abnormality results in a diagnosis of drug-induced liver injury (DILI)
 - Exceptions: Clinically nonsignificant, treatable, or reversible laboratory abnormalities including liver function tests, uric acid, etc.
- Any Grade 4 hematologic toxicity lasting ≥7 days, EXCEPT:
 - o Grade 4 thrombocytopenia of any duration
 - Grade 3 thrombocytopenia associated with bleeding that requires a platelet transfusion
- Febrile neutropenia Grade 3 or Grade 4 ONLY if:
 - Grade 3 is defined as ANC <1000/mm³ with a single temperature of >38.3
 °C (101 °F) or a sustained temperature of ≥38 °C (100.4 °F) for more than 1 hour
 - Grade 4 is defined as ANC <1000/mm³ with a single temperature of >38.3
 °C (101 °F) or a sustained temperature of ≥38 °C (100.4 °F) for more than 1 hour, with life-threatening consequences and urgent intervention indicated
- Prolonged delay (>2 weeks) in initiating the second cycle of anti-PD-1 therapy while on study due to lerapolturev-related toxicity.
- Prolonged delay (> 15 weeks) in initiating the second cycle of anti-PD-1 therapy while on study due to anti-PD-1-related toxicity (12 weeks for recovery to ≤ Grade

Confidential Page 54 of 109

1 and up to an additional 3 weeks for steroid taper of oral prednisone or equivalent to \leq 10 mg/day)

- Any treatment-related toxicity that causes the participant to discontinue treatment during the DLT evaluation period
- Grade 5 treatment-related toxicity

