5.5 Dose Modification/Toxicity Management Guidelines

5.5.1 Lerapolturev

For AEs related to lerapolturev, lerapolturev may be withheld or permanently discontinued based on the severity of the adverse reaction.

Confidential Page 65 of 109

Holding Lerapolturev Dosing

If a participant experiences any of the following toxicities deemed related to lerapolturev, lerapolturev administration should be held until the toxicity has resolved to at least CTCAE Grade 1 or has returned to baseline:

- Grade 2 or greater irAE, with the exception of vitiligo
- Grade 2 or greater allergic reactions
- any other Grade 3 or greater hematologic or non-hematologic toxicity

For participants receiving concurrent lerapolturev and anti-PD-1 therapy, lerapolturev and the anti-PD-1 therapy can be administered independently of each other where appropriate. Should the investigator determine an AE is related to anti-PD-1 therapy and not lerapolturev, continuation of lerapolturev injections is allowed (or vice versa). However, if the AE is determined to be related to the combination, this should be noted and treatment with both therapies should be held until resolution, as described above.

Permanent Discontinuation:

Lerapolturev should be permanently discontinued if any lerapolturev-related Grade 3 or greater hematologic or non-hematologic toxicity fails to resolve to Grade 1 or baseline OR occurs more than twice (ie, three episodes = permanent discontinuation).

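### Two dose-limiting toxicities defined by a late second anti-PD-1 cycle cannot be known when an Arm 2 participant is declared clear at 21 days

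*Protocol*

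**What the plan says.** Protocol Section 3.1.4 sets the window: "The DLT evaluation period begins on the day of first lerapolturev injection (ie, Cycle 1, Day 1) and ends 21 days later". The list that follows includes two events defined by lateness of the second anti-PD-1 cycle. One is tied to lerapolturev toxicity: "Prolonged delay (>2 weeks) in initiating the second cycle of anti-PD-1 therapy while on study due to lerapolturev-related toxicity". The other is tied to anti-PD-1 toxicity: "Prolonged delay (> 15 weeks) in initiating the second cycle of anti-PD-1 therapy while on study due to anti-PD-1-related toxicity". A further item covers stopping treatment and is the only one whose own wording confines it to the window: "Any treatment-related toxicity that causes the participant to discontinue treatment during the DLT evaluation period".

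For the weekly (QW) schedule, Section 3.1.3 has the data safety monitoring committee (DSMC) meet once 12 participants, six per arm, "have cleared the DLT evaluation period (ie, 21 days after Cycle 1, Day 1". At that meeting, "should an excessive DLT rate (ie, >33%) be detected", the committee may recommend a lower dose, fewer lesions or fewer weekly injections in one or both arms. SAP Section 1.1 repeats the 21-day timing. Neither document says how a delay is scored if it becomes established after the participant has been called clear.

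**The concern.** The clearance rule runs on the calendar, while two items on the list need more calendar time than the rule allows. Following Section 3.1.3 as written, an Arm 2 participant can be entered as DLT-free before that status can be known.

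The item of more than 2 weeks matters more. Most other entries in Section 3.1.4 need Grade 3 or worse. Apart from discontinuation inside the window, this item is the only route by which a lasting Grade 2 lerapolturev-related toxicity becomes a DLT. The protocol expects such toxicities to interrupt treatment. Section 5.5.1 holds lerapolturev for "Grade 2 or greater irAE, with the exception of vitiligo", and if an event is attributed to the combination, "treatment with both therapies should be held until resolution".

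At stake is how complete the DLT rate is at the one planned check on the new regimen. The maximum dose per visit had risen from 6 x 10^8 to 1.6 x 10^9 TCID50 (1.6 x 10^9 / 6 x 10^8 = 2.67-fold) and injections had become weekly for seven doses. The response-rate criterion and the sample size are not affected.

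**Working it through.** **Inputs.** The window ends 21 days after Cycle 1 Day 1 (Section 3.1.4). Anti-PD-1 starts on Day 1 (Tables 1 and 2, footnote 11). From the two schedules of assessments, the second anti-PD-1 dose is due on Day 15 (nivolumab every 2 weeks), Day 22 (pembrolizumab every 3 weeks), Day 29 (nivolumab every 4 weeks) or Day 43 (pembrolizumab every 6 weeks).

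**The plan's own timing.** Window end = 1 + 21 = Day 22. On the earlier schedule, combination dosing began on Day 10, and 10 + 21 = Day 31, which matches the 31 days given in Section 3.1.3 for that schedule.

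**Where delay starts.** It has to be counted from the due date. Counted from the previous dose, an on-time dose given every 3 weeks or less often would already exceed 2 weeks.

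**First day on which each item can be true.** More than 2 weeks late: due day + 14 + 1. More than 15 weeks late: due day + 105 + 1. Subtract 22 for the gap after the window closes.

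| Anti-PD-1 schedule | Due day | >2 weeks: first day | Gap (days) | >15 weeks: first day | Gap (days) |
|---|---|---|---|---|---|
| Nivolumab every 2 weeks | 15 | 30 | 8 | 121 | 99 |
| Pembrolizumab every 3 weeks | 22 | 37 | 15 | 128 | 106 |
| Nivolumab every 4 weeks | 29 | 44 | 22 | 135 | 113 |
| Pembrolizumab every 6 weeks | 43 | 58 | 36 | 149 | 127 |

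The first row is the case most favourable to the plan, because it counts the Day 15 dose as the second cycle although the nivolumab cycle is 4 weeks. The allowances of 2 days on the first anti-PD-1 dose and 7 days on a cycle only move these dates later.

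**Who is affected at the review.** The meeting is triggered when the last of the 12 reaches Day 22, so others will be further on. As an assumption, take one enrollment every 14 days. The protocol reports the run-in complete as of July 2021 and 11 participants randomized by 10 December 2021, which is roughly that pace. Counting back from the last participant, study days at the review are 22, 36, 50, 64 and so on (22 + 14j). The item of more than 2 weeks is then not assessable in the last one participant (threshold Day 30), the last two (Day 37 or 44) or the last three (Day 58), counting both arms; only those in Arm 2 matter. For the 15-week item, 22 + 14j is below 121 for j = 0 to 7 and below 149 for j = 0 to 9, so it is not assessable in 8 to 10 of the 12. A faster pace widens the gap and a slower one narrows it.

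**What one participant can change.** With six per arm, 2/6 = 33.3% and 3/6 = 50%. One late-qualifying event can move the arm from one to the other.

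**The case against.** A reader might infer that the delay items can never count, so that the 33% guide is blind to them. The documents do not support this. Section 3.1.4 limits only the discontinuation item to the window, which suggests that the others are not so limited. Section 9.1.5 has the DSMC review possibly related DLTs throughout the trial, with freedom to recommend dose changes.

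A reader might also attach a probability to a missed trigger. With six Arm 2 participants, a trigger of three and an assumed 40% rate of such delays, the binomial chance of reaching three is 46% if delays count and 0 if they do not and there are no other DLTs. That contrast depends on the weaker reading above and on a rate with no source. Table 3 reports lerapolturev-related events of any grade in 1 of 6 Arm 2 participants and 3 of 13 combination participants. Even if every one had been such a delay, the chance of three or more in six would be about 6% or 14%. Those data come from the earlier dose and schedule, so they do not settle the rate either.

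Three further limits stand:

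- The guide is discretionary and the committee sees all safety data, so a prolonged hold is visible whether or not it is labelled a DLT.
- Section 5.5.1 lets the two drugs be given independently, so a toxicity due to lerapolturev alone need not delay anti-PD-1.
- The note closing Section 3.1.3 counts an Arm 2 event only if it is lerapolturev-related and worse or more frequent than expected with anti-PD-1 alone, or if it resists usual management because of lerapolturev.

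These points reduce the consequence. They do not reconcile a 21-day clearance with items that take at least 29 days from Cycle 1 Day 1 to arise, and ongoing review of DLTs still requires knowing whether a late delay is one.

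**Conclusion.** The text is wrong as written, with limited effect; correcting it is worthwhile but not critical. Under every allowed anti-PD-1 schedule, both delay items lie outside the period after which a participant is called clear: by 8 to 36 days for the item of more than 2 weeks, and by 99 to 127 days for the item of more than 15 weeks. The 12-participant review can therefore set an Arm 2 DLT rate against 33% with these items not yet assessable in recently cleared participants. This conclusion rests on delay being counted from the due date and on the schedules in Tables 1 and 2. It does not show that the review would miss a real signal, and the documents give no basis for a probability that it would.

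**What to change.** Keep the 21-day window for onset of toxicity and add one sentence to Section 3.1.4:

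*A lerapolturev-related toxicity with onset in the DLT period that delays the second anti-PD-1 dose by more than 2 weeks past its due date is a DLT, whenever the delay is established.*

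Hold the 12-participant review on time. Report any Arm 2 participant with an unresolved anti-PD-1 hold at Day 22 to the DSMC as DLT status pending, and update the rate once the status is known. Making clearance wait for the outcome would be a poorer choice: neither Section 3.1.3 nor Section 9.1.5 pauses enrollment or dosing for the review, so the committee's look would be postponed just when a hold is unresolved.

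Move the 15-week item out of the DLT list and report such delays at the regular DSMC meetings. It concerns anti-PD-1 toxicity, while the list is introduced as events at least possibly related to lerapolturev, so it fits poorly there in any case.

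The cost is one sentence, one moved item and a status flag, with no new visits, data or participants and no delay to the review. The downside is that slightly more Arm 2 events may count as DLTs, which makes a recommendation to reduce dose or schedule somewhat more likely.
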